3.3.2 Potential Benefits

This research study includes procedures that may change the treatment patients with ADHD would otherwise receive. We hope the knowledge gained will be of benefit to the patients. While there may not be a direct benefit to the patients, it is hoped that the knowledge gained will benefit others in the future.

4 - Study Objectives

4.1 Hypothesis

In subjects with adult ADHD after Mydayis treatment (from end of single-blind placebo lead-in) there will be significant improvement in:

1) Overall symptoms of adult ADHD as measured by the total score on the Adult ADHD Investigator Symptom Rating Scale (AISRS) (primary effect).

2) Overall inattentive (IA) and hyperactive-impulsive (HI) ADHD symptom subsets on the AISRS and overall impairment via the Clinical Global Impression-Severity (CGI-S) scale.

3) Total ADHD symptoms fourteen hours after AM dosing as measured via total scores on the Time Sensitive Adult ADHD Symptom Scale (TASS); Inattentive (IA) and hyperactive-impulsive (HI) ADHD symptom subsets (TASS) subsets.

4) In neuropsychological measurement of Executive Function in the early evening (fourteen to fifteen hours after morning dosing) as measured by (WebNeuro: Verbal Interference/Stroop, Go/No-Go, CPT/TOVA)

5) In clinical symptoms of Executive Function in the early evening, as measured by the BRIEF-A.

4.2 Primary Objective

The primary objective of this proposal is to examine the efficacy of Mydayis on ADHD symptoms and executive function throughout the day into early evening, about 14-15 hours after first morning dosing. The primary measure of ADHD symptoms will be the total score on the AISRS, the Adult ADHD Investigator Symptom Rating Scale.

4.3 Secondary Objectives

The secondary objectives of this study are to examine the changes after Mydayis treatment in:

1. Overall inattentive (IA) and hyperactive-impulsive (HI) ADHD symptom subsets on the AISRS and overall impairment via the Clinical Global Impression-Severity (CGI-S) scale.

2. Total ADHD symptoms fourteen to fifteen hours after AM dosing as measured via total scores on the Time Sensitive Adult ADHD Symptom Scale (TASS) and the Inattentive (IA) and hyperactive- impulsive (HI) ADHD symptom TASS subsets.

3. Neuropsychological measurement of executive function in the early evening (fourteen to fifteen hours after morning dosing) as measured by (WebNeuro: Verbal Interference/Stroop, Go/No-Go, CPT/TOVA)

4. Clinical symptoms of executive function, as measured by the BRIEF-A.

5 - Study Design

5.1 General Design Description

Description of Study type

This will be a phase three, single-blind study, with a two-week, placebo lead-in and then a four-week forced titration treatment with Mydayis with starting dose of 12.5 mg/day with titration based on clinical response and potential adverse events.

Number and Description of Each Treatment Arm/Group

This will be a six-week trial after the screening period. After a two-week, subject singleblind, placebo lead-in, all patients will receive four weeks of Mydayis (12.5mg-37.5mg/day), with treatment order fixed. Study visits are hybrid; conducted remotely and in clinic.

Doses per Subject per Treatment

During the two-week, placebo lead-in, all subjects will receive 12.5mg Placebo at Visit 1 and Visit 2. During Visit 3, Mydayis treatment will be initiated at a dose of 12.5mg/day and will increase in increments of 12.5mg, based upon clinical response and tolerability, up to 25mg at Visit 4, up 37.5mg at Visit 5 and holding at the dose from visit 5 of up to 37.5mg at Visit 6. There will be no dispensation at Visit 7, which is the last in clinic/remote visit for this study. Patients will be seen weekly throughout the trial both in clinic and remote.

Our primary outcome is effects of Mydayis on overall adult ADHD symptoms via total AISRS Score. In secondary analyses, we will also analyze the following variables: Evaluation of ADHD subset IA and HI symptoms on the AISRS; TASS scores 1 hour, 4 hours and 14-15 hours post dose (total, inattentive and hyperactive-impulsive subsets) (for effects of Mydayis over time at different points of the day and within the day); expanded Adult ADHD Self Report Symptom Rating Scale (expanded-ASRS) Symptom Checklist (total, inattentive and hyperactive-impulsive, executive function and emotional control subsets); symptoms of executive function (BRIEF-A: GEC, metacognition, behavioral regulation scales and subscales: Inhibit, Shift, Emotional Control, Initiate, Working Memory, Plan/Organize, Organization of Materials, Monitor); and neuropsychological tests (WebNeuro: Verbal Interference/Stroop, Go/No-Go, CPT/TOVA): Response Time Variability [RVP], Response Time, d', Errors of Omission, Errors of Commission, Post-Commission Response Times, Multiple Responses, Anticipatory Responses).

Our statistical analysis framework will be the general linear regression model. We will choose the distributional family and link function based on the distribution of the outcome variables. Each regression model will predict the outcome as the dependent variable with weeks in trial after the end of the two-week, single-blind, placebo lead-in as the independent variable. All analyses will use the ITT sample. For our design, a significant effect of week assesses the significance of the drug effect. We have chosen an IIT analyses as we can include all patients except for placebo responders in the analyses. We have chosen a single-blind placebo lead-in to define placebo responders, which are defined as patients who experience \geq 30% decrease in their total AISRS scores during placebo lead-in treatment. Placebo responders will be discontinued from the study. We anticipate that, based on the literature, 10% or fewer of patients will be placebo responders and that the overall discontinuation rate in the trial will be 20%. Changes within the day in TASS ratings 1 hour post dose vs. 4 hours post dose vs. 14-15 hours post dose will also be analyzed via the general linear regression model. Correlations between ADHD and executive function ratings will be examined via Spearman's correlation coefficients.

Statistical Power Analysis

Justification for sample size:

Up to 50 patients will be enrolled to be sure that 32 evaluable patients reach the end of treatment at week six. The graph shows power at different values of the Cohen's d effect size for estimating the difference between baseline and endpoint values. For our primary analysis, which uses a two-sided test with a type I error of 0.05, it shows that 32 evaluable patients, will give a power of 90% or more for effect sizes of 0.6 or greater. 0.6 is a reasonable expectation for an effect size: it is half of the 1.2 effect size reported by *Spencer et al. (2008)* and thus is at the lower end of what we should expect to see in this study.

5.1.1 Study Date Range and Duration

The total expected length of the study from subject recruitment to follow-up is approximately 15-18 months. The individual recruitment from screening to the follow up GCP phone call will be approximately 7-8 weeks. Note: screenings/washouts can take a few weeks.

5.1.2 Number of Study Sites

This is an investigator-initiated protocol with funding from Shire. Shire will provide the investigational products Mydayis and placebo, in addition to some funding. This is a single site study, where all subjects are consented and all study activities are conducted in person and/or remotely at the address below.

NYU Langone Medical Center- Adult ADHD program

[name]

5.2 Outcome Variables

5.2.1 Primary Outcome Variables

The primary objective of this proposal is to examine the efficacy of Mydayis on ADHD symptoms and executive function throughout the day into the early evening-(14-15 hours after first morning dosing). This study will extend the evidence basis for Mydayis in adult ADHD to include efficacy with a clinical ADHD symptom measure validated for DSM-5 adult ADHD. The Spencer et al. (2008) and Weisler et al. (2017) studies used the ADHD-RS scale; the former using DSM-IV adult ADHD criteria and training for adult ADHD prompts. The Weisler et al. (2017) study embedded adult ADHD prompts into the ADHD-RS. Although the ADHD-RS with prompts has been widely utilized in ADHD trials, it not yet been fully validated for DSM-5. The Adult ADHD Investigator Symptom Rating Scale (AISRS) is a similar scale to the ADHD-RS with adult prompts, but it employs adult stem questions (as compared to the ADHD-RS using childhood stem questions), rates the 18 DSM symptoms of ADHD and has been validated for the DSM-5 (Silverstein MJ et al. 2018). It has also been used in multiple adult ADHD clinical treatment trials evaluating atomoxetine, droxidopa, and OROS methylphenidate (see section on scales) and its use in a Mydayis trial will further the comparison of Mydayis results with these agents. Another purpose of this trial is to re-examine the clinical efficacy of Mydayis later in the day on ADHD symptoms; the data on ADHD symptoms via the TASS (Spencer et al. 2008) is a decade old and has not been examined in subsequent trials. This study will specifically examine TASS ratings 14-15 hours after morning dosing. We have chosen 14-15 hours to allow comparison to neuropsychological measures which could not be completed later in the day in the clinic. A third purpose is extend the data on the effects of Mydayis on executive function to include neuropsychological measures of executive function and specific clinical scales of executive function.

Background/Rationale

Attention-deficit/hyperactivity disorder (ADHD) is a neuropsychiatric disorder characterized by problems with sustaining attention, organization, planning, procrastination, daydreaming, restlessness, impulsivity and hyperactivity. Adult ADHD is a common and highly impairing disorder affecting 4.4% of the US population (*Kessler RC et al. 2006*). Recent factor analyses (*Adler et al. 2017*) have highlighted the importance of co-travelling symptoms of executive function deficits (organization, planning, time

management and working memory) in addition to the core symptoms of inattention and hyperactivity-impulsivity noted in the DSM (DSM-5) (American Psychiatric Association 2013). Furthermore, it has been posited that executive function deficits define the impairment in ADHD (Barkley and Murphy 2010). Psychostimulants are a mainstay of pharmacotherapy for adult ADHD and five sustained-release preparations have been FDA approved for adult ADHD. One of these preparations, Mydayis, is a triple-beaded preparation of mixed amphetamine salts, which, in early studies, (Spencer et al. 2008) has been shown to have a clinical duration of up to 16 hours via the TASS scale and a documented efficacy on adult ADHD DSM-IV symptoms via the ADHD-RS (where training on use of adult ADHD prompts was given but not utilized with scale administration). Data from this study also supported some efficacy of Mydayis on cotravelling symptoms on executive function as measured by subsets of the Brown ADD Scale. However, specific executive function clinical scales and neuropsychological tests of executive function were not utilized, and executive function was not assessed later in the day. This proposal specifically addresses these issues by using the AISRS, an ADHD symptoms scale validated for DSM-5, re-assessing ADHD clinical symptoms later in the day via the TASS, and utilizing clinical scales (BRIEF-A) and neuropsychological tests (WebNeuro: Verbal Interference/Stroop, Go/No-Go, CPT/TOVA)

5.2.2 Secondary and Exploratory Outcome Variables

Exploratory Objectives: We will explore correlations of TASS ratings with AISRS ratings to examine overall ADHD ratings vs. ADHD ratings throughout the day. We will also explore correlations of changes in neuropsychological assessments of executive function (WebNeuro: Verbal Interference/Stroop, Go/No-Go, CPT/TOVA) versus changes in BRIEF-A measures. Furthermore, we will examine potential differential effects of Mydayis in the sample of patients who have defined executive dysfunctions (GEC score on BRIEF-A \geq 65 at placebo-baseline). We will also examine correlations in self-report of ADHD symptoms on the ASRS versus clinician report of ADHD symptoms on the AISRS, and also changes in self report measures of executive function and emotional dyscontrol on the ASRS versus these measures on the BRIEF-A.

5.3 Study Population

The study population will consist of males and females between the ages of 18-55, inclusive. They will be referred from area clinicians, NYU clinicians via EPIC (slicer dicer) and advertisements such as flyers, online search engine searches and StudyKIK.

The population must have ADHD and no comorbid psychiatric issues requiring treatment; exception for major depression, dysthymia and anxiety disorders in remission, but stable on psychiatric medications for three weeks or more at the discretion of the principal investigator

They should also meet all inclusion and not meet any of the exclusion criteria. In the opinion of the investigator, subjects must be of good health and a good candidate for a clinical research trial.

Up to 50 patients will sign consent and be screened, 34 will be enrolled into the singleblind placebo lead-in, and 32 patients will be randomized into the four-week treatment phase to be sure that at least 30-32 evaluable patients reach the end of treatment at week six.

Good clinical practices will ensure we call subjects one week after their last dose of study medication to ensure they are not experiencing any adverse events and have connected to treatment as usual in the community.

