The remaining 34 subjects will be randomized/enrolled into the treatment/placebo part of the study. During the two-week, placebo lead-in, if the subject has a 30% decrease in the AISRS, they will not move into the 4-week treatment period of the study.

We are aiming to have at least 32 subjects complete the study. The graph shows power at different values of the Cohen's d effect size for estimating the difference between baseline and endpoint values. For our primary analysis, which uses a two-sided test with a type I error of 0.05, it shows that 32 evaluable patients will give power of 90% or more for effect sizes of 0.6 or greater. 0.6 is a reasonable expectation for an effect size: it is half of the 1.2 effect size reported by Spencer et al. 2008 and thus is at the lower end of what we should expect to see in this study.

Number of Study Sites

This is an investigator-initiated protocol with funding from Shire. Shire will provide the investigational product MYDAYIS and PLACEBO in addition to some funding. This is a single site study, where all subjects are consented and all study activities are conducted remotely and/or at the address below.

NYU Langone Medical Center- Adult ADHD program [name]

Primary Outcome Variables

We will explore correlations of TASS ratings with AISRS ratings to examine overall ADHD ratings vs. ADHD ratings throughout the day into the early evening.

Secondary and Exploratory Outcome Variable

Exploratory Objectives: This study will explore correlations of TASS ratings with AISRS ratings to examine overall ADHD ratings vs. ADHD ratings throughout the day into early evening. The study will also explore correlations of changes in

of executive function Verbal neuropsychological assessments (WebNeuro: Interference/Stroop, Go/No-Go, Continuous Performance Test (CPT)/TOVA) versus changes in BRIEF-A measures. Furthermore, it will examine potential differential effects of Mydayis in the sample of patients who have defined executive dysfunctions (defined by a Global Executive Composite (GEC) score on BRIEF-A \geq 65 at placebobaseline). The study will also examine correlations in self-report of ADHD symptoms on the ASRS versus clinician report on the AISRS and also changes in self report measures of executive function and emotional dyscontrol on the ASRS versus these measures on the BRIEF-A.

Visit Schedule Tab	le		1	1			0	r	I
Description	Visit 1		Visit 2	Visit 3	Visit 4	Visit 5	Visit 6	Visit 7	тс

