6.4.3 Planned Analyses

6.4.3.1 Primary Analyses

Our statistical analysis framework will be the general linear regression model. We will choose the distributional family and link function based on the distribution of the outcome variables. Each regression model will predict the outcome as the dependent variable with weeks in trial after the end of the single-blind placebo lead-in as the independent variable. All analyses will use the ITT sample. For our design, a significant effect of week assesses the significance of the drug effect. We have chosen an IIT analyses as we can include all patients except for placebo responders in the analyses. We have chosen a single-blind placebo lead-in to define placebo responders, which are defined as patients who experience \geq 30% decrease in their total AISRS scores during placebo lead-in treatment and will be discontinued from the protocol. We anticipate that, based on the literature, 10% or fewer of patients will be placebo responders and that the overall discontinuation rate in the trial will be 20% (*Manor et al. 2012*). The changes within the day in TASS ratings, 1-hour post dose vs. 4 hours post dose vs. 14-15 hours post dose will also be analyzed via the general linear regression model. Correlations between ADHD and executive function ratings will be examined via Spearman's correlation coefficients.

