6.4.5 Handling of Missing Data

Missing outcome data will be handled in regards to analysis in the following way: last observation will be carried forward.

7 - Trial Administration

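### Thirty-four lead-in entrants and 20% overall discontinuation give about 27 completers, not 30-32, and the plan does not say which patients its power figure counts

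*Combined protocol and SAP*

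**What the plan says.** Section 5.3 gives the patient flow. Up to 50 sign consent and are screened, then "34 will be enrolled into the singleblind placebo lead-in, and 32 patients will be randomized into the four-week treatment phase", with at least 30-32 evaluable at the end of treatment. The Synopsis (Number of Participants) agrees on the lead-in number, "The remaining 34 subjects will be randomized/enrolled into the treatment/placebo part of the study", and sets the goal: "We are aiming to have at least 32 subjects complete the study". Section 5.3.1 repeats the 34 and gives the goal as 30-32.

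The attrition assumption is in sections 5.1, 6.4.1, 6.4.3.1 and 6.4.4: "10% or fewer of patients will be placebo responders and that the overall discontinuation rate in the trial will be 20" per cent. Section 5.1 adds: "Placebo responders will be discontinued from the study".

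The sample size justification in 5.1, repeated in 6.4.1, reads "Up to 50 patients will be enrolled to be sure that 32 evaluable patients reach the end of treatment at week six". It claims at least 90% power at d = 0.6 with 32 evaluable patients. Section 6.4.2 makes the same claim but gives the target as 32-30.

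On the analysis set, section 6.4.3.1 uses an ITT sample because "we can include all patients except for placebo responders in the analyses". For missing outcomes, section 6.4.5 says the "last observation will be carried forward".

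**The concern.** There are two linked problems.

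First, the completer target does not follow from the lead-in number and the expected attrition. Getting from 34 to 30-32 requires a much lower loss than the 20% that the statistical sections expect.

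Second, the N behind the power statement is not defined. The sample size text counts evaluable patients who reach the end of treatment, which points to completers. The planned analysis keeps everyone except placebo responders and fills in missing outcomes, so it also includes drop-outs from the treatment phase. Evaluable is not defined, and the three populations listed in 6.4.3.4 are not tied to the power calculation.

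A reader therefore cannot tell how many patients the primary analysis is expected to have, or whether the stated 90% applies to it. There is no slack to absorb the difference, because 32 is the smallest n that reaches 90% at d = 0.6.

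**Working it through.** **Inputs from the plan**

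- Two-sided alpha 0.05; Cohen's d = 0.6 for the baseline-to-endpoint difference; 32 evaluable patients; power at least 90% (5.1, 5.3.1, 6.4.1, 6.4.2).
- 50 consented, 34 into the lead-in, 32 into treatment, 30-32 at the end (5.3).
- At most 10% placebo responders, who are discontinued; 20% overall discontinuation (5.1, 6.4.1, 6.4.3.1, 6.4.4).

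**Step 1: the plan's own power figure.** For a paired t-test, power = P(|T| > t(0.975, n−1)), where T is noncentral t with n−1 degrees of freedom and noncentrality d√n. With n = 32 and d = 0.6 the noncentrality is 0.6 × √32 = 3.394 and the critical value is 2.040. Power is 0.908, so the claim reproduces. At n = 31 power is 0.898.

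**Step 2: the loss implied by the flow.** From 34 to 32 is 2/34 = 5.9%. From 34 to 30 is 4/34 = 11.8%. The stated 20% would be 0.20 × 34 = 6.8 patients.

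**Step 3: completers under the stated attrition**

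| Reading of the 20% | Arithmetic | Completers |
|---|---|---|
| Includes placebo responders | 34 × 0.80 | 27.2 |
| Applies to the 32 treated | 32 × 0.80 | 25.6 |
| Added to a full 10% responders | 34 × 0.90 × 0.80 | 24.5 |
| Ignored; 10% responders only | 34 × 0.90 | 30.6 |

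Only the last row reaches 30, and it drops the 20% altogether. The first row is the natural reading of an overall rate, since responders are themselves discontinued. It is also the most favourable reading that uses the 20%.

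**Step 4: chance of meeting the target.** With completers distributed as Binomial(34, 0.80), P(at least 30) = 0.162 and P(at least 32) = 0.023.

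**Step 5: power at d = 0.6, and d needed for 90% power, by n**

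| n | What it represents | Power | d for 90% |
|---|---|---|---|
| 34 | Analysis set, no responders | 0.924 | – |
| 32 | Plan's figure; analysis set, two responders | 0.908 | 0.592 |
| 31 | Analysis set, 10% responders (30.6 rounded up) | 0.898 | 0.602 |
| 30 | Analysis set, 10% responders (30.6 rounded down); lower completer target | 0.888 | 0.612 |
| 27 | Completers, 20% including responders | 0.851 | 0.648 |
| 25 | Completers, responders additional (24.5 rounded up) | 0.821 | 0.676 |
| 24 | Completers, responders additional (24.5 rounded down) | 0.804 | 0.691 |

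**Step 6: carried-forward values (assumption, not in the documents).** Take 31 analysed patients, of whom 27 complete and 4 carry forward a fraction of the effect. If that fraction is one half, the mean is 0.6 × 27/31 + 0.3 × 4/31 = 0.561. Mixing the two groups adds a little variance, so d is 0.558 and power is 0.853. If the fraction is 1.0, power stays at 0.898. The range is therefore about 0.85-0.90.

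**The case against.** The strongest reply is that the power claim has a reading consistent with the plan. If the two patients lost between 34 and 32 are placebo responders (5.9%, within the 10% ceiling), the analysis set is 32. Later drop-outs stay in it by carry-forward, and nominal power is 0.908. That is arithmetically right. But it works only with at most two responders, whereas the plan allows up to 10%. It also sets aside the sample size text, which ties evaluable to reaching the end of treatment, and it leaves the 30-32 completers unexplained.

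A second reply is that up to 50 are enrolled, so 20% loss leaves 40. Several sections do call the 50 enrolled. The Synopsis (Study Duration) and 5.3 make clear that these are consented patients before screening, and 5.3 puts 34 into the lead-in. This shows a labelling fault, not a larger trial. If the lead-in number is not meant as a limit, the plan should say so.

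Third, the practical loss is modest. The plan places d = 0.6 at the low end of what it expects, and 27 completers give 0.938 at d = 0.7. This stands, and it limits the seriousness of the point.

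Fourth, the appendix list names a separate statistical analysis plan and the power graph is not shown, so either might define the N. That is possible, but the available text does not define it, and neither could reconcile 34, 20% and 30-32.

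**Conclusion.** The concern holds. The stated yield of 30-32 completers is inconsistent with 34 lead-in entrants and 20% overall discontinuation; those figures give about 27. This takes the 20% to include placebo responders and to apply to the lead-in entrants. If responders are additional at the full 10%, the figure is 24-25.

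The 90% power claim is correct for 32 patients, but the plan does not establish that 32 will be available. At d = 0.6, power is about 85% for 27 completers, roughly 6 points below the 90.8% at n = 32. For the planned analysis set it is nominally 89-90% at a 10% responder rate, 1-2 points below, and 90% is kept with at most two responders. Dilution by carried-forward values could lower the second figure, but by how much rests on an assumption outside the documents.

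This should be corrected. It does not undermine the trial.

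**What to change.** Amend the Synopsis, 5.1, 5.3, 5.3.1, 6.4.1 and 6.4.2 so that they carry the same numbers:

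1. Label the 50 as consented throughout, and use 34 as the single lead-in number.
2. State whether the 20% overall discontinuation includes placebo responders.
3. Restate expected completers as about 27, with 24-25 as a sensitivity case if responders are additional.
4. Define evaluable, and say whether the power N is completers or the ITT set without placebo responders and with last observation carried forward. Restate power to match: about 85% at d = 0.6 for 27 completers (90% at d = 0.65), or nominally 89-90% for the 30-31 patients left at a 10% responder rate, noting that carried-forward values may lower this.

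The cost is wording, and a slightly less favourable stated power. No extra patients are needed. If the sponsor would rather keep 32 completers as the target, 20% loss implies 32 / 0.80 = 40 lead-in entrants. That fits within 50 consented only if no more than 10 fail screening, and it is the sponsor's choice, not a requirement of this point.
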